2.4.2 Presentation of treatments

The following treatment labels will be used in the tables and listings:

- efgartigimod PH20 SC
- placebo PH20 SC

In the general characteristics analysis, a grand total will be added to summarize all participants over treatments. Grand totals will be shown last.

2.4.3 Ordering in tables and listings

All tables will be presented per treatment, unless specified otherwise. In by-visit displays, worst-case will be shown last, if present.

In listings for general characteristics, results will be ordered by treatment and participant, unless specified otherwise.

All other listings will be ordered by treatment, participant, analysis visit, and time point, unless specified otherwise.

In tables showing several parameters, each parameter will begin on a new page and parameters will be sorted alphabetically, within the parameter category if applicable.

The efgartigimod PH20 SC treatment group will always be shown first, then the placebo PH20 SC treatment group.

	Statistical Analysis Plan	
ARGX-113-2004	Final analysis	Final 1.0 of 7NOV2023

3. GENERAL CHARACTERISTICS ANALYSES

3.1 PARTICIPANT DISPOSITION

The following participant data will be tabulated:

- The number of participants in each analysis set
- The number and percentage of participants by country and site
- The number and percentage of participants for each analysis visit.
- Descriptive statistics of the phase duration (see section 2.2.1), calculated as phase end date – phase start date + 1 day
- The number and percentage of screen failures, of participants randomized but not treated and of participants who completed or discontinued the trial as documented on the study termination page and the number and percentage of participants for each trial discontinuation reason (including reasons for screen failures).
- The number and percentage of participants who completed or discontinued the treatment as documented on the end of treatment page and the number and percentage of participants for each treatment discontinuation reason.
- The number and percentage of participants who roll over to study ARGX-113-2005.

All information collected in the CRF concerning treatment allocation and study and treatment discontinuation will be listed.

3.2 PROTOCOL DEVIATIONS AND ELIGIBILITY

The number and percentage of participants with major and minor protocol deviations will be tabulated overall and by class of deviation.

All available information concerning major and minor protocol deviations, violations on eligibility criteria, participants not treated and participants excluded from the efficacy analysis will be listed.

3.3 DEMOGRAPHIC AND OTHER BASELINE CHARACTERISTICS

3.3.1 Available data

The following parameters will be available:

- Demographics: sex at birth, age at informed consent, race, ethnicity, height, weight at baseline, year of birth, date of signing ICF.
- Baseline disease characteristics: date of diagnosis, history of splenectomy (yes versus no), receiving concurrent ITP therapies at baseline (yes vs. no), history of gastrointestinal bleeding (yes versus no + number of times), history of intracranial hemorrhage (yes versus no + number of times), history of hemorrhage for coagulation disorder (yes versus no + number of times), participant with chronic or persistent ITP, received prior ITP therapy (yes versus no), baseline platelet level, baseline SF-36 (v2), baseline PRO: FACT Th6 questionnaire (Total FACT Th6 score) and FACIT fatigue Scale (Total FACIT Fatigue score), WHO-classified bleeding events.

	Statistical Analysis Plan	
ARGX-113-2004	Final analysis	Final 1.0 of 7NOV2023

3.3.2 *Derivation rules*

The following parameters will be derived:

- Body mass index (BMI) at baseline (kg/m^2) = (body weight at baseline (kg)) / (height at screening (m))²
Note: The BMI will be recalculated and rounded as detailed in section 2.3.3, even when already available in the database.
- Age category at baseline: 18-<65 years; 65-<75 years; ≥ 75 years
- Weight category at baseline: <50 kg, 50-<75 kg, 75 – <100 kg, 100 – <125 kg, ≥ 125 kg
- Baseline platelet level category: ($<15 \times 10^9/\text{L}$ versus $\geq 15 \times 10^9/\text{L}$)
- Ethnicity category: Japanese versus non-Japanese (including Hispanic or Latino, Not Hispanic or Latino, and Not allowed to ask per local regulations)
- Region:
 - East Asia: China, Japan, Korea, Taiwan
 - Europe: EU and EEA countries, EFTA countries (Norway, Iceland, Liechtenstein and Switzerland) and UK
 - Latin America (LATAM): Mexico, Argentina, Chile
 - Middle East and Africa (MEA): Israel, Jordan, Tunisia, Turkey, South Africa
 - non-EU Central and Eastern Europe (non-EU CEE): Russia, Georgia, Serbia, Ukraine
 - North America: United States, Canada
 - Rest of the world: any countries not mentioned above
- Time since diagnosis (years): (date of ICF – date of initial diagnosis)/365.25. Partially missing dates of diagnosis will be imputed as follows:
 - Missing start day will be imputed with 1
 - Missing start day and month will be imputed with 1JAN

Note: Result will be rounded as detailed in section 2.3.3.

- Baseline WHO bleeding score category: No bleeding, Grade 1, \geq Grade 2, calculated as the maximum bleeding scale over the different body systems available at baseline.
- See section 3.5.2 for categories of type of ITP therapy.
- Number of prior ITP therapies: derived as the distinct number of equivalent ITP therapies (equivalent name, see also section 3.5.2) that stopped before first IMP dose date
- See section 4.1.2.3 for the definitions of ITP-PAQ, FACT Th6, FACIT and the WHO-classified bleeding events.
- Recruitment cohort: wave 1 (signed ICF before the protocol amendment 4 of 15Jul2022) / wave 2 (signed ICF after 15Jul2022)

	Statistical Analysis Plan	
ARGX-113-2004	Final analysis	Final 1.0 of 7NOV2023

3.3.3 *Presentation of results*

Demographics will be presented using descriptive statistics for age, height, weight and BMI at baseline, and frequency tabulations for age category, weight category at baseline, sex at birth, race, ethnicity, ethnicity category, region and recruitment cohort.

Baseline disease characteristics will be presented using descriptive statistics for:

- time since diagnosis
- platelet level
- SF-36 (v2): norm-based P-CS and M-CS scores
- total FACT-Th6 score
- total FACIT-Fatigue score
- number of prior ITP therapies
- number of types of prior ITP therapies

Baseline disease characteristics will be presented using frequency tabulations for:

- baseline platelet level category
- history of splenectomy
- receiving concurrent ITP therapies at baseline
- history of gastrointestinal bleeding
- number of events of gastrointestinal bleeding
- history of intracranial hemorrhage
- number of events of intracranial hemorrhage
- history of hemorrhage from coagulation disorder
- number of events of hemorrhage from coagulation disorder
- participant with chronic or persistent ITP
- received prior ITP therapy (yes/no), number of prior ITP therapies, number of prior ITP therapies received category (<3, ≥3)
- number of types of prior ITP therapies
- WHO bleeding score
- WHO bleeding score category

All demographic data and baseline disease characteristics will be listed. History of splenectomy, history of gastrointestinal bleeding, history of intracranial hemorrhage and history of hemorrhage of coagulation disorder will be shown on a separate listing specific for ITP history.

3.4 **MEDICAL HISTORY AND CONCOMITANT DISEASES**

3.4.1 *Available data*

Medical history findings are coded into system organ classes (SOC) and preferred terms (PTs) using the medical dictionary for regulatory activities (MedDRA), version 26.0. For each finding, a start and stop date or ongoing flag is collected.

	Statistical Analysis Plan	
ARGX-113-2004	Final analysis	Final 1.0 of 7NOV2023

For primary ITP history the following data are collected:

- Date of initial diagnosis
- Date of confirmation per American Society of Hematology (ASH) criteria
- Persistent/chronic ITP

In-patient hospitalization for the management of ITP during the study, for at least an overnight stay, is recorded separately. The hospitalization date and time of admission and discharge is collected.

3.4.2 Derivation rules

Medical history finding: not ongoing at screening, ended before date of signing informed consent

Concomitant disease: medical history condition still ongoing at screening

Duration of hospitalization (days):

- Date of discharge - date of admission + 1 day
- Study discontinuation date – date of admission + 1 day (when no date of discharge is available)

In this case the duration will be presented as “>x days” on the listing.

3.4.3 Presentation of results

Prior splenectomy events had to be captured as ITP therapy in the clinical database and will therefore not be shown in the medical history displays.

Medical history and concomitant diseases will be tabulated separately. Both tables will show:

- The number and percentage of participants with findings
- The number and percentage of participants with gastrointestinal bleeding, intracranial hemorrhage and coagulation disorder hemorrhage
- The number and percentage of participants with findings by SOC and PT

For hospitalizations for ITP management the following data will be shown:

- Incidence of hospitalizations
- Summary statistics of the duration of hospitalizations

All medical history, prior vaccinations, primary ITP history, concomitant disease data and hospitalizations will be listed.

3.5 PRIOR AND CONCOMITANT THERAPIES

3.5.1 Available data

All therapies are coded using the WHO-DRUG Dictionary version MAR2023 (Global) Format B3. Anatomical therapeutic chemical (ATC) selection is performed. The ATC coding up to level 4 is available in the clinical database. For each therapy, a start date or prior flag and stop date or ongoing flag are collected.

	Statistical Analysis Plan	
ARGX-113-2004	Final analysis	Final 1.0 of 7NOV2023

3.5.2 *Derivation rules*

Based on their start and stop date, therapies will be allocated into 1 or both of the following categories:

- Prior: any therapy that strictly started before the first IMP dose date.
- Concomitant: any therapy that was taken on or after the first IMP dose date.

A medication that started before the first IMP dose date and continued during the study will be classified as both prior and concomitant.

The ITP-specific therapies will be allocated to the following categories:

- Prior ITP therapy: stopped prior to first IMP dose date
- Continued concurrent ITP therapy: started prior to first IMP dose date and continued on or after first IMP dose date
- New concurrent ITP therapy: started on or after first IMP dose date or therapy of which the mean daily dose has increased compared to baseline

ITP therapy records with the same equivalent name will be combined to do the allocation in case the end and start date overlap or are subsequent, the start date of the next record being one day after the end date of the current record. For the combination of records, records with (partially) missing dates will be excluded. Therapies with (partially) missing dates will be allocated to each category unless the available parts of the therapy start or stop date or the started prior to trial/ongoing at end of trial flag provide evidence not to do so.

The type of ITP therapy will be allocated to the following categories according to the medical review performed by the sponsor: corticosteroids / IVIG, anti-D / fostamatinib / splenectomy / TPO-RA/ dapsone / danazol / anti-CD20 / other immunosuppressants. Therapies that cannot be assigned to any of these 9 categories will be categorized to type 'Other'.

Rescue ITP therapy will be allocated to the following categories:

- methylprednisolone, dexamethasone, prednisolone, prednisone: selection based on ATC4 = "H02AB"
- immunoglobulins given IV (IVIg): selection based on ATC4 = "J06BA"
- IV anti-D: selection based on CMDECOD = 'ANTI-D IMMUNOGLOBULIN', 'SPECIFIC IMMUNOGLOBULINS'
- platelet transfusions: selection based on CMDECOD = 'PLATELETS, CONCENTRATED'
- other: rescue medications that are not in any of the 4 previous categories

Occurrence of rescue therapy: a period of maximum 5 days where 1 or more rescue treatments are administered simultaneously or consecutively to the study participant. The start date/time of the occurrence is the start of the administration of the first rescue treatment. If this period exceeds the maximum of 5 days, a new occurrence will be assigned, with start date/time of the occurrence being the start date 5 days after the initial occurrence start date.

	Statistical Analysis Plan	
ARGX-113-2004	Final analysis	Final 1.0 of 7NOV2023

More information on the use of rescue therapy can be found in the CTP section 6.6.4.

3.5.3 *Presentation of results*

Non-ITP prior and concomitant therapies, including vaccines, will be tabulated (separately), by ATC class (level 1 and 3) and generic term.

Prior and concurrent ITP therapy will be tabulated by ATC class (level 1 and 3) and equivalent name (or generic term if 'other'). Rescue ITP therapies will be tabulated by category and generic term.

Prior ITP therapy and concurrent ITP therapy will also be tabulated (separately) by type of ITP therapy and equivalent name (or generic term if 'other').

All prior and concomitant therapies data will be listed with detailed information about ATC classes. Similarly, prior ITP therapy, concurrent ITP therapy, vaccines, and rescue ITP therapy will be listed separately.

3.6 **STUDY DRUG ADMINISTRATION**

3.6.1 *Available data*

For each study drug administration, the start and end date/times, and the volumes will be recorded.

Data on self-administration by participant or their caregiver will also be collected.

3.6.2 *Derivation rules*

The following parameters will be derived:

- Number of administrations: sum of all administrations of study drug.
- Compliance (%): $100 * (\text{number of doses received} / \text{number of doses expected})$; Compliance will be calculated over the 24-week treatment period and will take into account the weekly or every other week administration.

Notes:

- Dosing is expected at a visit except if the reason not done is due to biweekly administration, due to platelet count > 150 or platelet count > 400 or rescue therapy. As some of these reasons are entered as free text in the eCRF, the list of reasons not done will be reviewed by the sponsor and text to be considered as a valid reason will be flagged.
- For participants who discontinued early, visits on or after treatment discontinuation are not considered in the compliance calculation.
- Number and percentage of participants who ever switched to every other week dosing

	Statistical Analysis Plan	
ARGX-113-2004	Final analysis	Final 1.0 of 7NOV2023

- The dosing regimen is derived for each analysis visit until treatment discontinuation as follows:
 - The first 4 weeks (ie, baseline to week 3) are always considered as weekly.
 - Every other week dosing starts at the administration not done due to biweekly administration or at the performed visit subsequent to the one not done due to platelet count > 150 or platelet count > 400
 - Every other week dosing ends at the date of an administration not done due to rescue medication or at the date of the second of at least two consecutive administrations of a dose
 - All other administrations done in between every other week periods are considered as weekly.

Note: reasons for not dosing can contain free text and will therefore be categorized by the sponsor. This categorization will be used for the derivation of the dosing regimen.

- Fixed dosing regimen (weekly, every other week): derived for participants still being dosed at or after CRF visit 17:
 - Weekly: if participant received rescue therapy during the period of 28 days prior to visit 16
 - Else, the dosing regimen will equal the dosing regimen at analysis week 16
- Cumulative duration of every other week dosing: number of weeks for which the participant was on the every other week dosing regimen
- Percentage of time of every other week dosing: $100 * (\text{cumulative duration of every other week dosing} / \text{number of weeks up to and including week 24})$. Weeks after treatment discontinuation will not be considered.
- completing training: the final outcome for a participant/caregiver is considered completed if the participant/caregiver had passed at least 4 trainings in the last 10 weeks between analysis week 14 and 23 and is being considered capable at least once after 4 or more trainings

3.6.3 *Presentation of results*

Overall number of administrations, compliance, number of participants who ever switched to every other week dosing, cumulative duration of every other week dosing and dosing regimen between week 17 and 24 will be summarized using descriptive statistics.

	Statistical Analysis Plan	
ARGX-113-2004	Final analysis	Final 1.0 of 7NOV2023

A frequency table will be created showing IMP training information, for participants and caregivers separately:

- The number and percentage of participants/caregivers receiving training (using as denominator the total number of participants per treatment group in the safety analysis set)
- Total number of training visits received per participant/caregiver. Express as number and percentage of participants/caregivers receiving 1, 2, 3, etc. trainings (using as denominator the total number of participants/caregivers that received training per treatment group in the safety analysis set)
- Number and percentage of participants/caregivers considered capable to perform self-administration during at least one training visit (using as denominator the total number of participants/caregivers that received training per treatment group in the safety analysis set)
- Minimum number of training visits required by participant/caregiver to be considered capable for first time to perform self-administration. Express as number and percentage of participants/caregivers requiring 1, 2, 3, etc. trainings (using as denominator the total number of participants/caregivers that received training per treatment group in the safety analysis set).
- Number and percentage of participants/caregivers completing training. The denominator is the total number of participants per treatment group in the safety analysis set.

All study drug administration data and self-administration training data (by participant and caregiver) will be listed.

	Statistical Analysis Plan	
ARGX-113-2004	Final analysis	Final 1.0 of 7NOV2023

4. EFFICACY, PHARMACOKINETIC, PHARMACODYNAMIC AND IMMUNOGENICITY ANALYSES

4.1 EFFICACY

4.1.1 Available data

Efficacy will be assessed using platelet count, WHO-classified bleeding events, PROs (FACIT-Fatigue, FACT-Th6), QoL (SF-36, ITP-PAQ), [REDACTED]

4.1.2 Endpoints and derivation rules

All efficacy endpoints will be analyzed on the overall FAS population or a subset of participants in the FAS with chronic ITP. For all references to weeks, analysis visits are considered as described in section 2.2.4 unless specified otherwise. If multiple assessments fall within the same analysis window, only the assessment closest to the target date will be considered unless specified otherwise. Other assessments within this window will only be listed and not considered in the below analyses. Only the time to response endpoint (see section 4.1.2.3) will be derived using all possible measurements and not only the one closest to the target of the analysis visit. Only visits during the treatment phase will be considered for defining the different responses and time to response parameters.

4.1.2.1 PRIMARY ENDPOINT

The primary endpoint is the proportion of participants with a sustained platelet count response (week 19 – 24) within the adult population with chronic ITP.

A participant is considered a responder, ie, has a sustained platelet count response, if he/she shows platelet counts of at least $50 \times 10^9/L$ for at least 4 of the 6 analysis visits between weeks 19 and 24 of the study. ($\geq 50 \times 10^9/L$ prim resp).

The main analysis on the primary endpoint will use the ‘composite variable strategy’ in case of main intercurrent events using the Cochran-Mantel-Haenszel test (see also section 4.1.3.2). This strategy implies that when a main intercurrent event occurs, a participant is considered a non-responder, if the participant has not achieved sustained platelet count response before the occurrence of the main intercurrent event. This happens in the following situations:

- early discontinuation of treatment (prior to week 24) due to lack of efficacy (DSDECOD = “Lack of efficacy”) or due to an AE
- initiation of rescue therapy at week 12 or later: relative day of start date of rescue medication \geq lower limit ADY of analysis visit corresponding to Week 12

	Statistical Analysis Plan	
ARGX-113-2004	Final analysis	Final 1.0 of 7NOV2023

- increase of dose and/or frequency of concurrent ITP therapies or start of a new concurrent ITP therapy at week 12 or later:
 - (if start date concurrent ITP therapy \geq lower limit ADY of analysis visit corresponding to Week 12) and (dose > previous dose of the specific ITP therapy OR frequency > previous frequency of the specific ITP therapy)
 - AND
 - (if start date concurrent ITP therapy \geq lower limit ADY of analysis visit corresponding to Week 12) and (dose > dose of the specific ITP therapy at baseline OR frequency > frequency of the specific ITP therapy at baseline)
 - OR
 - new ITP therapy

Note: if for frequency a change is detected, but it is not clear whether a real increase has taken place, it will be considered worst-case and analysed as increase (e.g.: Baseline value 'QD' changed to e.g. 'at will', 'as needed'; Baseline value 'As needed' changed to e.g. 'QD', 'continuous'). Dose and frequency will always be considered in combination (ie, mean daily doses will be compared).

Missing values for reasons other than the main intercurrent events, will be imputed as described in section 4.1.2.5 (approach 1).

A complementary analysis for this primary analysis will use the 'treatment policy strategy' where these main intercurrent events are handled differently.

The occurrence of the intercurrent event is irrelevant: the values for the platelet counts are used regardless of whether or not the intercurrent event occurs. For this strategy the data will be used as is, without taking into account intercurrent events. Missing values for reasons other than the main intercurrent events, will be imputed as described in section 4.1.2.5 (approach 1).

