9.5.5.2. Handling of Main Intercurrent Events

A composite strategy approach will be taken to address the main intercurrent events described previously. This implies that participants who discontinue treatment before visit 24 due to lack of efficacy (eg, more than 3 occurrences of rescue therapy) or due to an AE, as well as participants who receive rescue therapy at week 12 or later, or for whom dose and/or frequency of concurrent ITP therapies have increased at week 12 or later, will be considered nonresponders for the primary endpoint analysis.

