1.2 STUDY ENDPOINTS

1.2.1 *Primary endpoint*

The primary endpoint is the proportion of patients with chronic ITP with a sustained platelet count response defined as achieving platelet counts of at least $50 \times 10^9/L$ for at least 4 of the 6 visits between week 19 and 24 of the study.

Participants who discontinue treatment prior to visit 24 due to lack of efficacy (e.g. more than 3 occurrences of rescue therapy) or due to an AE, and who have not achieved sustained platelet count response between week 19 and 24, are considered non-responders. Participants who receive rescue therapy at week 12 or later, or for whom dose and/or frequency of concurrent ITP therapies have increased at week 12 or later, are also considered non-responders.

1.2.2 *Secondary endpoints*

Key Secondary Efficacy Endpoints Subject to Alpha Control:

- Extent of disease control defined as the number of cumulative weeks over the planned 24-week treatment period with platelet counts of $\geq 50 \times 10^9/L$ in the chronic ITP population.
- Proportion of patients in the overall population (chronic and persistent ITP) with a sustained platelet count response defined as achieving platelet counts of at least $50 \times 10^9/L$ for at least 4 of the 6 visits between week 19 and 24 of the study.
- Proportion of patients in the overall population achieving platelet counts of at least $50 \times 10^9/L$ for at least 6 of the 8 visits between week 17 and 24 of the study.
- Incidence and severity of the WHO-classified bleeding events in the overall population.

Other Secondary Endpoints Not Subject to Alpha Control (overall population):

- Proportion of patients with overall platelet response defined as achieving a platelet count of $\geq 50 \times 10^9/L$ on at least 4 occasions at any time during the 24-week treatment period.
- Extent of disease control defined as the number of cumulative weeks until week 12, with platelet counts of $\geq 50 \times 10^9/L$.

	Statistical Analysis Plan	
ARGX-113-2004	Final analysis	Final 1.0 of 7NOV2023

- Proportion of patients with overall platelet response defined as achieving a platelet count of $\geq 50 \times 10^9/L$ on at least 4 occasions at any time until week 12.
- Mean change from baseline in platelet count at each visit.
- Time to response defined as the time to achieve 2 consecutive platelet counts of $\geq 50 \times 10^9/L$.

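### Protocol 9.5.5.2, SAP 1.2.1 and SAP 4.1.2.1 give three different rules for late intercurrent events in the primary endpoint, and the legible change log does not record the difference

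*SAP*

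**What the plan says.** A sustained response is a platelet count of at least 50×10⁹/L at four or more of the six analysis visits in weeks 19 to 24. Three sections say what an intercurrent event does to it.

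- **Protocol 9.5.5.2.** A composite strategy with no condition. It covers "participants who discontinue treatment before visit 24 due to lack of efficacy" or an adverse event, rescue at week 12 or later, and participants whose concurrent ITP therapies "have increased at week 12 or later, will be considered nonresponders for the primary endpoint analysis". Protocol 4.1 and 6.6.1 are equally unconditional for concurrent therapy started or increased from week 12.
- **SAP 1.2.1.** Participants who discontinue for those reasons "and who have not achieved sustained platelet count response between week 19 and 24, are considered non-responders". Rescue and therapy increase carry no condition: those participants, including those whose therapies "have increased at week 12 or later, are also considered non-responders".
- **SAP 4.1.2.1.** One rule is given for every such event: "a participant is considered a non-responder, if the participant has not achieved sustained platelet count response before the occurrence of the main intercurrent event". The condition comes before the list of events and governs all three.

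SAP 4.1.2.2 applies the 4.1.2.1 strategy to key secondary endpoints 2 and 3. SAP 4.1.3.2 analyses data missing because of an event as non-response but refers back to 4.1.2.1, so it does not settle the matter.

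Protocol section 9 allows minor changes in statistical methods without an amendment, provided the SAP documents them as changes from the protocol. The legible text of SAP 6.1 records the stratified CMH analysis, extra analyses and the PK analysis set. It does not record this change.

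**The concern.** The primary endpoint is the gatekeeper for the whole testing hierarchy, and its estimand treats these events as failures. The SAP derivation can credit a response to a participant whom the protocol defines as a failure, and the SAP's own endpoint section disagrees with the derivation on rescue and therapy increase. SAP 1.8 calls for independent programming of this endpoint. Two programmers could each follow the SAP and classify the same participant differently. If that surfaces after unblinding, the rule would be chosen with the result in view.

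**Working it through.** **The rules applied to the same data.** Each case starts with counts of at least 50×10⁹/L at weeks 19, 20, 21 and 22.

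| Later event | Protocol 9.5.5.2 | SAP 1.2.1 | SAP 4.1.2.1 |
|---|---|---|---|
| Rescue in week 23 | non-responder | non-responder | responder |
| Discontinuation for an adverse event before visit 24 | non-responder | responder | responder |

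SAP 1.2.1 is also ambiguous for an earlier discontinuation. Take a participant who stops treatment at week 15, keeps attending weekly visits as Protocol 7.1 provides, and has four qualifying counts in weeks 19 to 24. Read literally, SAP 1.2.1 makes this a responder, while SAP 4.1.2.1 and the protocol do not. If SAP 1.2.1 means a response achieved before discontinuing, the two SAP sections agree on this case.

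**When the exemption can act.** Four of the six visits must qualify first, so the earliest fourth qualifying visit is week 22. For key secondary endpoint 3 (six of eight visits, weeks 17 to 24) the sixth is also week 22 at the earliest (17 + 5). From SAP Table 4, the week-22 target is 29 + 18×7 = day 155 and its window opens on 26 + 18×7 = day 152. The schedule allows visits up to 2 days late and a platelet count within 1 day of the procedure, so day 152 needs an unscheduled count. Visit 24 is day 162 and end of treatment is day 169.

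- Discontinuation before visit 24: days 155 to 161, about 7 days (10 from day 152).
- Rescue up to end of treatment: days 155 to 169, about 15 days (18 from day 152).
- Therapy increase for insufficient response: cannot qualify, because Protocol 6.6.1 requires four weeks with no count of 30×10⁹/L or more. A label-based dose increase of an oral TPO-RA still could.

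Late rescue also needs a fall from at least 50 to below 30×10⁹/L, plus bleeding or bleeding risk, wet purpura, or urgent surgery (Protocol 6.6.4).

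**The plan's own figure.** Inputs from Protocol 9.3: N = 180, 2:1 allocation (120 and 60), 21.8% versus 5%, Fisher's exact test, one-sided 0.025. Exact enumeration gives power of 85.2%, which agrees with the stated minimum of 80%.

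**Illustration of size.** Expected responders are about 0.218×120 = 26 and 0.05×60 = 3. Each reclassified efgartigimod participant moves that arm's rate by 1/120 = 0.83 percentage points. The number reclassified is an assumption; 0 to 4 is shown as a range.

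| Efgartigimod responders reclassified | Table | One-sided Fisher p |
|---|---|---|
| 0 | 26/120 vs 3/60 | 0.0024 |
| 4 | 22/120 vs 3/60 | 0.0100 |

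The planned test is a stratified CMH, so these p-values show scale only. Placebo responders could be reclassified too, which would move the result the other way.

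**The case against.** Protocol section 9 lets the SAP refine methods, the exemption acts only in the closing days of treatment, and crediting a response already completed is a defensible choice. All of that stands. The exemption is not wrong in itself, but a permitted change has to be logged, and logging alone would leave SAP 1.2.1 and 4.1.2.1 in conflict.

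A reader might infer four stronger points that the documents do not support:

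- **Restoring the protocol rule takes power below 80%.** This would require the 21.8% to have been obtained with the exemption. Protocol 9.3 says only that it rests on rates observed in ARGX-113-1801, not which rule produced them.
- **Nothing planned would reveal the effect.** SAP 4.1.2.4 and a number of efficacy table titles are redacted. SAP 8 also plans a table of intercurrent events in chronic ITP, and listings of response outcomes, platelet counts and rescue therapy, from which affected participants could be found. What is absent from the legible text is a test under the protocol rule: the stated complementary analysis uses treatment policy.
- **The differing cut-offs change results.** SAP 1.2.1 has "Participants who discontinue treatment prior to visit 24 due to lack of efficacy", as in the protocol, while SAP 4.1.2.1 has "early discontinuation of treatment (prior to week 24) due to lack of efficacy". But visit 24 is the last possible dosing visit, so little remains to discontinue between it and week 24. This is a wording mismatch.
- **Counting the start of a new ITP therapy is a further departure.** Protocol 4.1 and 6.6.1 already count it.

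**Conclusion.** The contradiction is in the text and needs no assumption: three sections give three rules for the gatekeeper endpoint, and two key secondary endpoints inherit the most permissive one. The derivation departs from the protocol estimand, and that departure is not logged in legible text.

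The practical reach is small: few participants are likely to be affected and the documents give no number. Neither the net direction nor the effect on the test is known, and no loss of significance or power is claimed. The two p-values above rest on the planning rates and an assumed reclassification in one arm. The point should be fixed because it concerns how the primary endpoint is defined and because settling it before unblinding is cheap.

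**What to change.** Before unblinding:

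1. Apply the protocol rule in the main analysis. In SAP 4.1.2.1, delete the conditional clause that ends "a participant is considered a non-responder, if the participant has not achieved sustained platelet count response before the occurrence of the main intercurrent event", from the word *if* onward. In SAP 1.2.1, delete the matching condition that opens "and who have not achieved sustained platelet count response between week 19 and 24, are considered non-responders", keeping the statement that these participants are non-responders. Key secondary endpoints 2 and 3 follow by cross-reference.
2. Keep the conditional version as a complementary analysis and report the number reclassified per arm.
3. If the sponsor prefers the exemption, word it identically in SAP 1.2.1 and 4.1.2.1, log it in SAP 6.1 as a change from the protocol, and add the protocol rule as a sensitivity analysis.
4. Use one discontinuation cut-off, visit 24 or week 24, in Protocol 9.5.5.2, SAP 1.2.1, SAP 4.1.2.1, key secondary endpoint 1 in SAP 4.1.2.2, and SAP Tables 8 and 9.

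Separately, log in SAP 6.1 that key secondary endpoint 1 discounts counts for only 4 weeks after each rescue, with no week-12 limit. Protocol 9.5.5.1 and 9.5.6 discount all counts after rescue at week 12 or later. For example, rescue at week 13 with qualifying counts only at weeks 18 to 24 scores 7 under the SAP and 0 under the protocol.

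The cost is a few clause edits, log entries and a small amount of extra analysis. The observed response rate may be slightly lower.
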